Objectives:	
Primary Objective
 
Part 1:
 
To determine the optimum dose of ASLAN003 monotherapy based on the efficacy, safety and tolerability profile in Acute Myeloid Leukemia (AML) patients who are ineligible for standard therapy. 
Part 2:
 
To provide a preliminary estimate of the efficacy of ASLAN003 at the optimum dose selected from Part 1. 
Secondary Objective
 
Part 1:
 
To evaluate the pharmacokinetics (PKs) of ASLAN003 and its metabolite LAS186558 in patients with AML. 
Part 2:
 
To further assess the safety and tolerability data of ASLAN003 at the optimum dose selected from Part 1. 
Exploratory Objectives:
 
To examine the myeloid differentiation effects of ASLAN003 using assays including but not limited to an ex vivo flow cytometry assay.To explore possible relationships between molecular abnormalities and measures of clinical response in patients with AML.

Study Design:	
This is a multicenter, single arm, non-randomised Phase IIA Study to evaluate ASLAN003 as a monotherapy in patients with AML.
 
AML patients who are ineligible for standard treatment including, but not limited to the following conditions, will be enrolled in the study:
 
• Newly diagnosed patients who are ineligible for standard therapy i.e., standard dose induction chemotherapy and reduced dose chemotherapy;• Patients with relapse from prior remission;• Patients with failed response to prior therapy including chemotherapy, hypomethylating agents, and bone marrow (BM) transplantation. 
Up to a total of 18-24 patients will be enrolled into this study - 6 patients in each dose cohort. The planned sequence of cohort enrollment is 100 mg QD - 200 mg QD - 100 mg BID. Furthermore, an additional cohort of 200 mg BID may also be enrolled, subject to agreement from the steering committee (SC) based on a review of safety data from the 100 mg BID cohort. A SC meeting will be set up and will meet to review all clinical information, including efficacy, safety and PK data obtained from this Study. Details of the SC outcome will be specified in the SC charter.
 
An expansion cohort of 20 patients (Part 2) will be recruited to study the optimum dose selected by the SC. The optimum dose will be selected from at least one cohort showing tolerable safety profile and clinical benefit in disease presentation. Details will be specified in the SC charter.
 
Patients with especially high blast cell count should be closely monitored for a possible differentiation syndrome. Investigators could manage suspected patients proactively according to the recommendations in the National Comprehensive Cancer Network (NCCN) guidelines acute promyelocytic leukemia (APL) differentiation syndrome section.
 
Bone marrow aspiration samples (BMA) will be collected before the first day of treatment, will be cultured in vitro and incubated with ASLAN003 to examine the efficacy of ASLAN003 ex vivo. Molecular studies will also be done to check for any phenotypic and genotypic changes in the patients' BM sample. A BM aspiration smear will be collected and processed locally before the first day of treatment. Ex vivo assay and molecular assessment will be processed centrally (Please refer to the BMA lab manual for details). This will be done in selected sites to be determined by the Sponsor.
 
All patients will continue to receive ASLAN003 until disease relapse, treatment failure, unacceptable toxicity, withdrawal of consent or death.

----------------------	--

	
18-24 AML patients ineligible for standard treatment (Part 1)
 
 ASLAN003 100mg QD[◇] 6 patients (completed) ASLAN003 200mg QD[◇] 6 patients ASLAN003 100mg BID[◇] 6 patients ASLAN003 200mg BID[△] 6 patients 
Expansion cohort* 20 patients (Part 2)
 
◇ If showing clinical benefit in the patient, ASLAN003 will be continued until disease progression, development of unacceptable toxic effects, or withdrawal of consent. △ An additional cohort of 6 patients in ASLAN003 200mg BID may commence once steering committee review all safety data in ASLAN100mg BID cohort showing tolerability signals. * An expansion cohort of 20 patients will be recruited to study the optimum dose selected by the steering committee.
 
Abbreviations: AML = acute myeloid leukemia; QD = once daily, BID = twice daily.

Number of patients:
	
Up to a total of 18-24 patients are planned to be enrolled in Part 1 of this Phase IIA study to be conducted in Australia, Singapore and other countries.
 
Approximately 20 patients are planned to be enrolled in the expansion cohort of Part 2 of this Phase IIA study to be conducted in Australia, Singapore and other countries.

Study Population:
	
Inclusion Criteria
 
Patients who meet all of the following criteria are eligible for enrollment in the study:
 
 1. Patients who are of or older than the legal age in the respective countries at the time when written informed consent is obtained 2. Patients who are able to understand and willing to sign the informed consent form (ICF) 3. Patients who are diagnosed with AML according to the 2016 revision to the World Health Organization classification of myeloid neoplasms and acute leukemia (refer to Appendix 1: WHO Classification of Acute Myeloid Leukemia) 4. Patients who have a sufficient archival or fresh BM aspiration sample for the evaluation of relevant exploratory endpoint. 
Note: Patients who do not have sufficient archival BM aspiration sample and refuse to repeat the procedure may be enrolled in the trial only after written confirmation by ASLAN

5. Patients who are ineligible for standard treatment of AML including but not limited to the following conditions:
 - Newly diagnosed patients who are ineligible for standard therapy namely standard dose induction chemotherapy and reduced dose chemotherapy;
 - Patients who relapsed from prior remission;
 - Patients who failed to respond to prior therapy including chemotherapy, hypomethylating agents, and bone marrow transplantation.
6. Patients who have an ECOG performance status of ≤ 2
7. Patients with adequate renal and hepatic function, as defined below:
 - Estimated Glomerular Filtration Rate (eGFR) or creatinine clearance (CrCl) (CrCl calculated by the Cockcroft and Gault method) ≥ 40 ml/min/1.73 m²
 - Total bilirubin, AST, and ALT $\leq 1.5 \times$ ULN

Exclusion Criteria:

Patients with any of the following criteria will be excluded from the study:

1. Patients who are diagnosed with *de novo* myeloid sarcoma without BM involvement
2. Patients who are diagnosed with acute promyelocytic leukemia/retinoic acid receptor alpha (*PML-RARA*)
3. Patients who received any other standard or investigational treatment for their leukemia within the last 7 days before starting the first dose of study drug, with the exception of leukapheresis and hydroxyurea
4. Patients with unresolved serious toxicity (\geq CTCAE 4.03 Grade 2) from prior administration of standard or investigational treatment for their leukemia
5. Patients who have a positive test for human immunodeficiency virus (HIV), viral hepatitis C infection (patients with sustained viral response are not excluded), active viral hepatitis B infection (positive hepatitis B surface antigen [HBsAg]) with hepatitis B virus deoxyribonucleic acid (DNA) exceeding 2000 IU/ml
6. Patients who have a known history of liver cirrhosis Child-Pugh score B or C
7. Patients who have any history of other malignancy unless in remission for more than 1 year (skin carcinoma and carcinoma-in-situ of uterine cervix treated with curative intent is not exclusionary)
8. Female patients who are pregnant or breast-feeding
9. Patients with a known history of alcohol or drug addiction on the basis that there could be a higher risk of non-compliance to study treatment per Investigator's discretion

	
10. Patients with a history or presence of a clinically significant condition which in the opinion of the Investigator could jeopardize the safety of the patient or the validity of the study results
 
11. Patients who have been previously treated with ASLAN003


Study Endpoints:
	
Primary Endpoints:
 
Part 1:
 
 • The primary objective of determining the optimum monotherapy dose of ASLAN003 in AML patients is based on the following endpoints: 
 ○ Overall Complete Remission Rate (OCRR): Defined as the proportion of patients with a best response of complete remission (CR) or complete remission with incomplete hematologic recovery (CRi), defined in accordance with the International Working Group (IWG) Response Criteria in AML. ○ Safety and tolerability: Based on AEs, safety assessments (including vital signs, electrocardiogram [ECG] parameters, clinical laboratory tests) and treatment exposure/dose intensity. 
Part 2:
 
 • Overall Complete Remission Rate (OCRR) 
Secondary Endpoints:
 
 • Efficacy (Parts 1 and 2): 
 ○ Relapse Free Survival (RFS): Defined as the time the criteria for remission (CR or CRi) are first met until there is evidence of patient relapse, regardless of whether the patient is still taking study drug. Relapse is defined as: 
 ➤ The reappearance of leukemic blasts in the peripheral blood or > 5% blasts in the BM not attributable to any other cause; ➤ The appearance of new dysplastic changes; ➤ The reappearance of or development of cytologically proven extramedullary disease; ➤ The reappearance of a cytogenetic or molecular abnormality. ○ Clinical Benefit Rate (CBR): defined as the proportion of patients with an AML IWG best response of CR, CRi or PR. ○ % change from baseline in BM blasts at Day 29. • Safety and tolerability (Part 2 ONLY): 
 ○ Based on AEs, safety assessments (including vital signs, electrocardiogram [ECG] parameters and clinical laboratory tests) and treatment exposure/dose intensity.

	
 ● Pharmacokinetics (Part 1 ONLY): If estimable, the following parameters will be calculated on Days 1 and 8, Cycle 1: 
 ○ PK parameters for ASLAN003: maximum observed plasma concentration (C_{max}), C_{max} at steady state ($C_{max ss}$), trough plasma concentration (C_{trough}), time corresponding to occurrence of C_{max} (t_{max}), and $C_{max ss}$ ($t_{max ss}$), AUC over the dosing interval (AUC_{tau}), AUC_{tau} at steady state ($AUC_{tau ss}$), terminal elimination half-life ($t_{1/2}$), effective elimination half-life at steady state ($t_{1/2 eff}$), apparent total clearance of the drug from plasma after oral administration (CL/F), apparent volume of distribution at steady state after oral administration (V_{ss}/F), accumulation ratio for AUC ($RacAUC$) and accumulation ratio for C_{max} ($RacC_{max}$). ○ PK parameters for LAS186558: C_{max}, C_{trough}, t_{max}, AUC_{tau}, $t_{1/2}$, $t_{1/2 eff}$, $RacAUC$, $RacC_{max}$, metabolic ratio (MR) for C_{max} (MRC_{max}) and AUC (MRAUC). 
Exploratory Endpoint (Parts 1 and 2):
 
 ● Assessment of the degree of blast cell differentiation by ASLAN003 using assays including but not limited to ex vivo flow cytometry assay using selected myeloid cell markers (such as CD11b). ● Assessment of the molecular abnormalities of AML blast cells at baseline.

Study Treatment:
	
Part 1: Patients will be administered with the study drug, ASLAN003. The starting dose of ASLAN003 is 100 mg QD given orally (PO). The maximum dose for optimum dose determination is 200 mg BID. It is recommended to administer ASLAN003 with food or within 30 minutes after food intake.
 
Part 2: An optimum dose selected by the SC from Part 1 is given orally (PO). It is recommended to administer ASLAN003 with food or within 30 minutes after food intake.
 
Visit Schedule: In order to address the primary objectives of the study, if treatment is interrupted for any reason, it is important that all planned safety and efficacy assessments are performed at the scheduled time, regardless of whether the patient is receiving study treatment, or not, at the time.

Study Duration:
	
Screening Period: 28 days

	
Treatment Period: All patients will receive a continuous 28-day treatment cycle of ASLAN003 until disease relapse, treatment failure (defined as failure to achieve a PR or higher within 4 cycles), development of unacceptable toxicity, withdrawal of consent or death.
 
Follow-up Period: All patients will be required to complete a safety follow-up visit within 28 days after the last dose of study treatment. All patients achieving CR or CRi will be followed for survival every 12 weeks post end of treatment (EOT) until disease relapse or death (in the absence of disease relapse) to find out the RFS.
 
The planned duration of entire study (treatment and follow-up) is approximately 2 years.

Study Assessments:
	
The schedule of the assessment for the study is provided in Table 1.
 
Safety Assessments: Patient safety will be evaluated based on the incidence of AEs and serious AEs (SAEs), physical examination, vital signs (blood pressure [systolic and diastolic], heart rate, respiratory rate, weight, and body temperature), ECG parameters, and clinical laboratory tests (hematology, clinical chemistry, coagulation and urinalysis).
 
All AEs will be evaluated according to NCI-CTCAE 4.03 and will be captured from the time of informed consent and continued until the safety follow-up assessment (28 days after last administration of study treatment). For the purpose of this study, fluctuations of pre-existing conditions that do not represent a clinically significant exacerbation or worsening are not to be considered AEs.
 
Pharmacokinetic Assessments (Part 1 ONLY): The blood samples for determination of plasma concentration of study drug will be collected on Day 1 and Day 8 at the following timepoints of Cycle 1 for QD regime: pre-dose, 1, 2, 4, 5, 6, 8, and 24 hours post dose.
 
In BID regime i.e 100mg BID and 200mg BID the PK sampling will be done at following timepoints: pre-dose, 1,2, 4, 5, 6, 8, and 12 hours (or evening pre-dose).
 
The plasma concentration-time data will be used to calculate the PK parameters for ASLAN003 and metabolite.” Part 2: will be determined by SC if needed.

	
Efficacy Assessments: For patients who do not have a sufficient archival of BM aspiration sample, a BM aspiration will be performed during Screening.
 
Efficacy will be evaluated with BM aspiration and peripheral blood based on the IWG Criteria for AML (Cheson, 2003) every 4 weeks, on Day 1 of every cycle from Cycle 2 to Cycle 5 and every 12 weeks thereafter. Patients who have already achieved CR can omit the BM aspiration at subsequent assessments if there is a normal complete blood count with differential of the peripheral blood. Investigator may perform additional efficacy assessment if required based on clinical judgment. Bone marrow aspiration smears will be processed locally.
 
Note: If treatment is interrupted for any reason, the scheduled efficacy assessments should be performed at the intended time point, regardless of whether the patient is currently receiving study treatment. Repeat assessments at the resume of treatment may be performed at the investigator’s discretion.
 
Other Assessments: Assays including but not limited to ex vivo flow cytometry assay using selected myeloid cell markers (such as CD11b) will be performed to assess the degree of blast cell differentiation upon treatment with ASLAN003. The percentage of CD11b positive cells will be determined before and after ex vivo treatment with ASLAN003. Molecular abnormalities of AML patients will also be assessed using polymerase chain reaction (PCR) or next-generation sequencing (NGS) The ex vivo assay and molecular assessment will be processed centrally (Please refer to the BMA lab manual for details).

Prohibited Medications
	
Any approved or investigational treatment given for the purpose to treat the leukemia, including but not limited to chemotherapy, hypomethylating agents, herbal medicine, Chinese medicine, leukapheresis, etc. will be prohibited during the study.
 
For the management of leukocytosis, hydroxyurea use per site practice is allowed for patients with peripheral blast count more than 20,000 cells/uL in the first two weeks of study treatment. Once the peripheral blast count drops to less than 20,000 cells/uL, site is required to discontinue with hydroxyurea to ensure no impact on efficacy readout. Hydroxyurea use is allowed for suspected or confirmed differentiation syndrome.


Statistical Analysis:
	
Part 1: The proposed design has been selected to provide an assessment of the efficacy, safety and tolerability of different doses of ASLAN003 in

	
patients with AML, whilst limiting the number of patients exposed to experimental treatments and procedures. Up to a total of 18-24 patients will be recruited in the study.
 
Part 2: The study is not formally powered. The sample size of 20 patients has been selected to provide further efficacy and tolerability data at the selected dose level, prior to conducting larger randomized trials.
 
Methods of Analysis: There are no formal statistical analyses planned. All primary and secondary endpoints will be listed and summarized using appropriate descriptive statistics and graphical displays. Safety will be assessed in the safety population and efficacy will be assessed in the evaluable for response (EFR) population.
 
Furthermore, waterfall plots of the % change from baseline in BM blasts at Day 28, and the best % change from baseline in BM blasts will be presented.
 
Pharmacokinetics: Concentrations and PK parameters will be listed and summarized using descriptive statistics in tables and graphs, as appropriate.

--	--

Table 1: Schedule of Study Assessments

Study Visit	Screening	Study Treatment Period							End of Treatment	Safety Follow-up	Survival Follow-Up
		Cycle 1					Cycle 2	Subsequent Cycles			
Treatment Cycles (28 days per cycle)	Day -28 to 0	Day 1	Day 8	Day 10	Day 15	Day 22	Day 1	Day 1	EOT	28 days after last administration of study medication	Every 12 weeks post EOT for RFS
Study Days		NA	±1	+1	±2	±2	±2	±2			
Study Allowed Window	NA	NA	±1	+1	±2	±2	±2	±2	Within 7 days of last dose of study treatment	±7	±7
General and Safety Assessments											
Informed Consent	X										
Eligibility Criteria	X	X									
Demographics	X										
Medical History	X										
Physical Examination	X	X	X		X	X	X	X	X	X	
Vital Signs (blood pressure, heart rate, respiratory rate, temperature)	X	X	X		X	X	X	X	X	X	
12-Lead Electrocardiogram	X				X		X		X	X	
Eastern Cooperative Oncology Group Performance Status (ECOG)	X	X							X		
Body weight	X	X					X	X	X		

Study Visit	Screening	Study Treatment Period							End of Treatment	Safety Follow-up	Survival Follow-Up
		Cycle 1					Cycle 2	Subsequent Cycles			
Treatment Cycles (28 days per cycle)	Day -28 to 0	Day 1	Day 8	Day 10	Day 15	Day 22	Day 1	Day 1	EOT	28 days after last administration of study medication	Every 12 weeks post EOT for RFS
Study Days		Day 1	Day 8	Day 10	Day 15	Day 22	Day 1	Day 1			
Study Allowed Window	NA	NA	±1	+1	±2	±2	±2	±2	Within 7 days of last dose of study treatment	±7	±7
Adverse Events/Serious Adverse Events ^a	X	X	X		X	X	X	X	X	X	
Prior and Concomitant Medication	X	X	X		X	X	X	X	X	X	
Laboratory Assessments											
Serum / urine β-human Chorionic Gonadotropin ^b	X								X		
Hematology	X	X	X		X	X	X	X	X		
Clinical Chemistry, Urinalysis ^c	X	X	X	X ^d	X	X	X	X	X		
Serology ^e	X										
Coagulation ^f	X				X				X		
Blood Pharmacokinetics Sampling ^g		X	X								
Bone Marrow Aspiration ^h	X						X	X			

Study Visit	Screening	Study Treatment Period							End of Treatment	Safety Follow-up	Survival Follow-Up
Treatment Cycles (28 days per cycle)	Day -28 to 0	Cycle 1					Cycle 2	Subsequent Cycles	EOT	28 days after last administration of study medication	Every 12 weeks post EOT for RFS
Study Days		Day 1	Day 8	Day 10	Day 15	Day 22	Day 1	Day 1			
Study Allowed Window	NA	NA	±1	+1	±2	±2	±2	±2	Within 7 days of last dose of study treatment	±7	±7
Other Assessment											
Survival status contact by phone ⁱ											X
Study Drug Administration											
ASLAN003		X	X	X	X	X	X	X			

Abbreviations: ALT = alanine aminotransferase; AST = Aspartate aminotransferase; CR = complete remission; CRi = complete remission with incomplete hematologic recovery; DNA = deoxyribonucleic acid; eCRF = electronic case report form; EOT = end of treatment; HBsAg = hepatitis B surface antigen; HBV = hepatitis B virus; NA = not applicable; PK=pharmacokinetics; RFS = relapse free survival.

Footnotes:

- a. Adverse event collection starts at the time of informed consent and continues until 28 days after the last administration of study drug. If a patient never receives study drug, but experience AE after informed consent form is signed, ONLY events the Investigator assessed as may have been caused by a study specific protocol procedure will be reported in eCRF.
- b. Serum or urine pregnancy test to be performed at the Screening visit for all females except those surgically sterile or 2 years postmenopausal. Serum or urine pregnancy tests will be performed at EOT. Unscheduled serum or urine pregnancy tests are allowed at the Investigator’s discretion.
- c. Screening clinical laboratory tests (clinical chemistry, urinalysis and coagulation) must be completed from Day -28 to 0. Screening clinical laboratory tests may be used in lieu of pre-treatment, Cycle 1 Day 1 tests, if performed within 1 week prior to the first administration of study drug.
- d. **ONLY AST, ALT and total bilirubin to be performed on Cycle 1 Day 10.**
- e. Serology tests must be completed from Day -28 to 0. If HBsAg result indicate active infection then test HBV DNA.
- f. Coagulation laboratory test will be performed at Screening, Cycle 1 Day 15 and EOT visit, however the Investigator may perform coagulation tests at other visits if required based on clinical judgment.

- g. Blood samples for PK analysis of ASLAN003 and LAS186558 for QD regime include: Day 1 and Day 8: pre-dose, 1, 2, 4, 5, 6, 8, and 24 hours post dose. In BID regime i.e 100mg BID and 200mg BID the PK sampling will be done at following timepoints: pre-dose, 1, 2, 4, 5, 6, 8, and 12 hours (or evening pre-dose). For Part 2- Steering Committee will decide whether PK analysis is required or not and ASLAN pharmaceuticals will be updated accordingly.
- h. Bone marrow aspiration is mandatory to be performed every 4 weeks on Day 1 of every cycle from Cycle 2 to Cycle 5 and every 12 weeks thereafter. Patients who have already achieved CR could omit the bone marrow aspiration at subsequent assessments if there is a normal complete blood count with differential of the peripheral blood. The Investigator may perform additional monthly bone marrow aspirate if required based on clinical judgment. Bone marrow aspiration smear will be processed locally. ONLY BMA collected during screening visit will be used to perform *ex vivo* assay and molecular assessment centrally (Please refer to the lab manual for details).
- i. Survival follow-up by either telephone or clinic visit will be performed in patients achieving CR or CRi every 12 weeks post EOT until disease relapse or death (in the absence of disease relapse) to enable the assessments of RFS.
- j. Cycle 2 Day 1 corresponds to day 29 of the study treatment.

TABLE OF CONTENTS

PROTOCOL SYNOPSIS	2
TABLE OF CONTENTS	15
LIST OF ABBREVIATIONS AND DEFINITIONS OF TERMS	19
1 INTRODUCTION	22
1.1 Disease Background	22
1.2 Currently Available Treatments for Acute Myeloid Leukemia	23
1.3 ASLAN003 (The Investigational Drug)	24
1.3.1 Pre-clinical Pharmacology of ASLAN003	24
1.3.2 Safety Pharmacology of ASLAN003	25

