1.1 Disease Background

AML, a heterogeneous hematologic malignancy, is the most common acute leukemia among adults and characterized by abnormal proliferation and differentiation of a clonal population of myeloid blasts in the bone marrow (BM) and peripheral blood. AML accounts for 25% of all leukemia of adults in the Western world, with the highest incidence rates occurring in the United States, Australia and Europe.² In 2016 in the United States, about 19,950 people were diagnosed with AML and 10,430 patients died from this disease. The median age of diagnosis is at 67 years and the incidence increases with age, with 54% of patients diagnosed at ≥ 65 years and approximately a third diagnosed at ≥ 75 years of age.³ In Australia, AML accounts for about 1.1% of all cancer cases annually;⁴ an age-standardized incidence rate of 3.8 per 100,000 persons: 4.7 per 100,000 persons in males and 3.0 per 100,000 persons in females is reported as per 2014 overview.⁵ The incidence of AML in the white population (3.8 per 100,000 person) is higher than that of the Asian population (3.2 per 100,000 person).⁶ According to the Singapore Cancer Registry 2015, myeloid neoplasms were the 10th most common cancer amongst males in Singapore in 2008-2012; and AML was the most common myeloid neoplasm accounting for 35.9% of 1,434 cases.⁷ In the majority of cases, AML develops as a *de novo* malignancy in previously healthy individuals. Many environmental factors, underlying hematological diseases (e.g. myelodysplasia) and prior chemotherapy for solid tumors or hematologic malignancies increase the risk of developing AML.^{3,8}

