1.5 Known or Potential Risks Associated with ASLAN003

ASLAN003 has demonstrated an acceptable safety profile in nonclinical toxicology studies and completed Phase I studies in humans. However, as with any new investigational drug, unexpected AEs may occur with the use of ASLAN003. The following is a summary of potential risks; additional details are presented in the IB:

- ASLAN003 must not be administered to pregnant or nursing women.
- ALT, AST, and total bilirubin along with signs or symptoms of liver toxicity should be monitored during ASLAN003 treatment.

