6.3.1.12 Laboratory Variables

Laboratory assessments will be performed locally at each center's laboratory by means of their established methods. Before starting the study, the Investigator will supply IQVIA/Sponsor with a list of the normal ranges and units of measurement.

The laboratory variables that will be assessed in accordance with the schedule of procedures described in Table 1 are summarized in Table 3.

The Investigator must review Screening laboratory results for patient eligibility prior to enrolling.

Laboratory tests can be repeated earlier than the next scheduled consecutive study visit at the Investigator's discretion and any associated safety issue should be followed up as per the Investigator's clinical judgment until resolution/stabilization.

In the event that the laboratory parameters show a significant shift from baseline values, patients will then be scheduled for an interim visit within 2 weeks to repeat the laboratory measurements.

Table 3: Laboratory Assessment

Hematology:	RBC count MCV MCH Leucocyte differential count Blasts Promyelocytes Myelocytes Metamyelocytes Band Neutrophils Segmented Neutrophils Eosinophils Basophils Lymphocytes Monocytes Platelets WBC count Hemoglobin Hematocrit	Urinalysis:	pH Protein Glucose Ketone Bilirubin Blood Leukocyte esterase Nitrite
Coagulation	INR aPTT		
Clinical Chemistry:	Albumin Creatinine Calcium Glucose Triglycerides Urea Uric acid Cholesterol HgbA1c Potassium Sodium Alkaline phosphatase GGT AST ALT Total bilirubin	Bone Marrow Aspiration	Aspiration site Cellularity Blasts Promyelocytes Myelocytes + Metamyelocytes Band + Segment Erythroid series Mono-histiocytes Eosinophils Plasma cells Lymphoid cells Miscellaneous Auer rods Dysplastic change Cytochemical
Serology*:	HIV HBsAg HBV DNA if positive HBsAg HCV antibody		
Pregnancy Test:	Serum or urine pregnancy test will be performed at the Screening and end of treatment visits for all females except those surgically sterile or 2 years postmenopausal. Subsequent serum or urine pregnancy tests are allowed at the Investigator's discretion.		

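### Pregnancy tests are required only at Screening and after the last dose, with none fixed at first dose or during treatment

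*Protocol*

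**What the plan says.** **Required tests.** The β-hCG row of protocol Table 1 is marked at Screening and at EOT only. Footnote b says: "Serum or urine pregnancy test to be performed at the Screening visit for all females except those surgically sterile or 2 years postmenopausal", and then "Serum or urine pregnancy tests will be performed at EOT". Beyond that, "Unscheduled serum or urine pregnancy tests are allowed" when the investigator sees fit. Table 3 in section 6.3.1.12 agrees: "Serum or urine pregnancy test will be performed at the Screening and end of treatment visits". The visit lists match. The test appears in 7.2.1 (Screening) and 7.2.3 (EOT), and in none of 7.2.2.1 to 7.2.2.6, which cover Cycle 1 Day 1, the later Cycle 1 visits, and Day 1 of every subsequent cycle.

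**Rules that depend on pregnancy status.** Section 1.5 states "ASLAN003 must not be administered to pregnant or nursing women". Pregnancy is exclusion criterion 8 (4.2) and a mandatory reason to withdraw a patient from study drug (4.3, 6.3.1.11). Section 6.3.1.11 says that nothing is known about the drug's effect on human fetal development. It requires contraception from before entry until 3 months after therapy, and immediate notification of a known or suspected pregnancy.

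**Timing.** Screening may fall up to 4 weeks before Cycle 1 Day 1 (7.2.1). The EOT visit follows the end of dosing, within 7 days of the last dose (7.2.3). The Table 1 row "Eligibility Criteria" is marked at Screening and again at Cycle 1 Day 1.

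**The concern.** The protocol makes pregnancy both a bar to the first dose and a reason to stop drug during treatment, but its fixed tests serve neither purpose well. The first may be four weeks old when dosing starts. The second comes when there is no drug left to stop. Eligibility is reviewed again at Cycle 1 Day 1 without a new test to support that review for criterion 8.

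The stake is patient and fetal safety. A site that follows the schedule exactly could give the first dose on an outdated negative result. It also need not test for a pregnancy that arises on treatment and raises no suspicion until after the last dose. Nothing statistical is at stake: no endpoint, estimate or analysis set is affected.

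**Working it through.** The plan states no figure to reproduce on this point. The check is a reading of the schedule plus calendar arithmetic.

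**Inputs**
- Screening test: Day -28 to Day 0 (Table 1), up to 4 weeks before first dose (7.2.1).
- Cycle length: 28 days (Table 1).
- Treatment failure: no partial remission or better within 4 cycles (3.4). Responders continue until relapse.
- EOT visit: up to 7 days after last dose (7.2.3).
- Visit window for Day 1 of Cycle 2 onward: ±2 days (Table 1).
- Planned enrollment: 18–24 in Part 1 and 20 in Part 2 (4.4).

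**Step 1. Do other provisions close the gap?** Footnote c of Table 1 lets Screening laboratory results replace Cycle 1 Day 1 tests only if they are at most 1 week old, but it names chemistry, urinalysis and coagulation, not hCG. So the pregnancy result may be 28 days old at first dose. Serology has the same latitude (footnote e: "Serology tests must be completed from Day -28 to 0"), but in this protocol serology is an entry check only, whereas pregnancy is also a stopping criterion on treatment.

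**Step 2. Required tests between first and last dose.** None.

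**Step 3. Time from Screening test to last dose** (to within a day, depending on how Day 0 is counted)

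| Treatment | Test on Day 0 | Test on Day -28 |
|---|---|---|
| One cycle | 0 + 28 = 28 days | 28 + 28 = 56 days |
| Four cycles | 0 + 4 × 28 = 112 days | 28 + 4 × 28 = 140 days |

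Measured to the EOT test instead, the four-cycle maximum is 28 + 112 + 7 = 147 days. For responders there is no fixed upper limit. These are gaps between fixed tests, not durations of undetected pregnancy.

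**Step 4. The same intervals with a test on Day 1 of each cycle.** The result at first dose is 0 days old. Successive Day 1 tests are 28 days apart, at most 28 + 2 + 2 = 32.

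**Step 5. How many women?** The documents do not say. The only age figure is for AML in general: "The median age of diagnosis is at 67 years and the incidence increases with age" (1.1). Enrollment totals 18 + 20 = 38 to 24 + 20 = 44. Assuming 2–10% are women of childbearing potential, the range is 0.02 × 38 = 0.76 to 0.10 × 44 = 4.4, or about 1 to 4 women.

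**The case against.** The schedule reads as described; the case on the other side is about weight and detail.

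- **Contraception already covers both intervals.** It is required before entry, so it applies between Screening and first dose too. The standard is strict: apart from abstinence, a barrier must be combined with another method. SAP 5.2 tracks lapses from the start of screening as important deviations. This lowers the probability of pregnancy, but it detects nothing.
- **Other on-treatment controls exist.** There are frequent clinic visits with adverse event review, the investigator may test at any time, and a suspected pregnancy must be reported at once. The withdrawal rule therefore still works. What remains is a possible delay in detection, because none of these controls requires a test.
- **The number of women is assumed.** This stands. The 2–10% has no source in the documents, patients are described as generally older (1.6), and zero cannot be excluded.
- **A lighter fix is possible.** A negative result within 7 days of first dose would match the limit in footnote c and avoid repeating a test done the day before. It would cut the oldest result at first dose from 28 to 7 days, but alone it adds nothing during treatment.
- **The tested population is not worded consistently.** Footnote b exempts surgically sterile women, while 6.3.1.11 counts a woman with a tubal ligation as of childbearing potential. This is a fair drafting point, and the amendment should settle it. It does not affect the conclusion.

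**Conclusion.** The concern holds. Exclusion 8 does rest on a mandatory test, but one that may be 28 days old at first dose. The on-treatment withdrawal rule has no required test behind it and relies on contraception, patient report and discretion. The gap to last dose is 28 to 56 days for one cycle, 112 to 140 days for four, and longer for responders. These gaps follow from the schedule alone; the estimate of 1 to 4 women rests on the assumed 2–10%. The practical effect is slower detection in a small group, possibly nobody, with potentially serious consequences for any fetus exposed. The change is worth making because it is cheap and supports rules the protocol already sets; the trial's results do not depend on it.

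**What to change.** Amend Table 1 (β-hCG row and footnote b), Table 3, 7.2.2.1 and 7.2.2.6 to require a urine or serum pregnancy test on Cycle 1 Day 1 and on Day 1 of every later cycle for women of childbearing potential, with the result known before dosing. Keep the Screening and EOT tests. Use the definition in 6.3.1.11 for the whole row, so that women with a tubal ligation are handled the same way at every visit.

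**Cost.** One simple test per cycle: 4 for a four-cycle patient (Day 1 of Cycles 1–4), or 4 × 1 = 4 to 4 × 4 = 16 across the study under the assumed 1 to 4 women, and none if no such woman is enrolled. Blood and urine are already scheduled on Day 1 of each cycle. If Screening urinalysis stands in for the Cycle 1 Day 1 sample, a fresh urine sample or one extra tube at the hematology draw is needed. A dose may have to be held while a positive result is confirmed. No visit, staff or invasive procedure is added.
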